7.2.2 SCORD Scoring

The Scoring Atopic Dermatitis (SCORAD) tool is well established in Dermatology to provide a numeric assessment of the degree and severity of dermatitis in atopic dermatitis. Recently, this tool was modified to assess the severity of dermatitis in CTCL patients undergoing mechlorethamine treatment (Alexander-Savino 2022). This score is calculated as:

- the percent of CTCL lesion showing dermatitis
- the severity of the dermatitis on a 3-point scale (0-none, 1-mild, 2-moderate, 3-severe) for redness, oozing/crusting, scratch marks, skin thickening, and dryness
- the patient's self-reported assessment of itch

The scoring form for SCORD is attached in Appendix 20.2 [APPENDIX II – SCORD Calculation Worksheet](#) on page [69](#).

7.2.3 *Patient Reported SAEQ Score*

The Skin Adverse Event Questionnaire is a series of patient self-reported assessments of application site events over the last 24 hours recorded in a visual analog scale (VAS) format and reported as a score of 0 to 10 as shown in Appendix 20.4 [Appendix IV - Skin Adverse Event Questionnaire](#). The number of application sites experiencing these symptoms will be noted. Symptoms specifically queried are:

- Rash
- Tenderness
- Pain
- Burning
- Swelling
- Redness
- Blistering
- Change in color

7.3 Clinical Laboratory Tests

7.3.1 *Hematology*

The hematology panel will be performed at the Central Laboratory. The panel will consist of the following tests:

- Red blood cell count (RBC)
- Hematocrit
- Hemoglobin
- Mean corpuscular volume (MCV)
- Mean corpuscular hemoglobin (MCH)
- Mean corpuscular hemoglobin concentration (MCHC)
- Platelet count
- White blood cell count (WBC)

- Percent and absolute neutrophil count
- Percent and absolute lymphocyte count
- Percent and absolute monocyte count
- Percent and absolute eosinophil count
- Percent and absolute basophil count

7.3.2 Clinical Chemistry Laboratory Tests

The clinical chemistry panel will be performed at the Central Laboratory. The panel will consist of the following tests:

The panel will consist of the following tests:

- Serum sodium
- Serum potassium
- Serum chloride
- Serum bicarbonate (CO₂)
- Alanine aminotransferase (ALT)
- Aspartate aminotransferase (AST)
- Total bilirubin
- Total protein
- Serum creatinine
- Blood urea nitrogen (BUN)
- Alkaline phosphatase

7.4 Vital Signs

Vital signs obtained will consist of:

- Resting Blood Pressure
- Heart Rate
- Respiratory Rate

8 STUDY DRUG MANAGEMENT

8.1 HyBryte

8.1.1 *Formulation*

HyBryte will be supplied in plastic screw-top jars containing 25 grams of 0.25% hypericin ointment (2.5 mg/gram). Jars are stored at room temperature.

8.1.2 *Storage*

HyBryte can be kept at room temperature (23 to 27°C, 73 to 81°F). HyBryte should be mixed with an applicator (eg, tongue depressor) prior to application.

8.1.3 *Packaging and Shipment*

HyBryte will be supplied in plastic screw-top jars containing 25 grams of 0.25% hypericin ointment (2.5 mg/gram). Jars will be labeled with the study number (HPN-CTCL-04), a jar identification number, the designation "Topical HyBryte (0.25% hypericin)", and the warning "Caution: New Drug-Limited by U.S. Federal Law to Investigational Use."

8.1.4 *Dose and Administration*

Patients randomized to the HyBryte treatment arm will be instructed to mix and apply the study drug to cover the entire surface of each lesion in a thin layer. However, application to uninvolved skin should be as limited as possible. The amount of ointment used for each application will be dependent upon the amount of lesion surface area. The patient should wear disposable gloves and wash their hands after applying the study ointment. If someone else helps apply the study ointment, they should wear disposable gloves. If the medicine gets on the skin of other people, they will be instructed to wash with soap and water.

8.2 Valchlor

Commercially available Valchlor will be used as the active comparator in this trial. Valchlor will not be provided by Soligenix and will be obtained by the site. All information below is extracted from the approved Valchlor package insert which should be followed for all storage, handling and administrations instructions. If there are discrepancies between this protocol and the approved Valchlor package insert, the package insert should prevail and be followed by the site (this will not be considered a protocol deviation)

8.2.1 Formulation

The active ingredient in Valchlor is mechlorethamine. Each tube of Valchlor contains 60 g of 0.016% w/w mechlorethamine clear gel (equivalent to 0.02% mechlorethamine HCl).

8.2.2 Storage

Prior to dispensing, store in the freezer at -13°F to 5°F (-25°C to -15°C). Advise patients that refrigerated storage is required once dispensed.

8.2.3 Packaging and Shipment

Valchlor is supplied in 60 g tubes of 0.016% w/w mechlorethamine as a clear gel.

8.2.4 Dose and Administration

Apply a thin film of Valchlor gel once daily to affected areas of the skin.

Stop treatment with Valchlor for any grade of skin ulceration, blistering, or moderately-severe or severe dermatitis (ie, marked skin redness with edema). Upon improvement, treatment with Valchlor can be restarted at a reduced frequency of once every 3 days. If reintroduction of treatment is tolerated for at least one week, the frequency of application can be increased to every other day for at least one week and then to once daily application if tolerated.

Valchlor is a cytotoxic drug. Follow applicable special handling and disposal procedures. Patients must wash hands thoroughly with soap and water after handling or applying Valchlor. Caregivers must wear disposable nitrile gloves when applying Valchlor to patients and wash hands thoroughly with soap and water after removal of gloves. If there is accidental skin exposure to Valchlor, caregivers must immediately wash exposed areas thoroughly with soap and water for at least 15 minutes and remove contaminated clothing.

Patients or caregivers should follow these instructions when applying Valchlor:

- Apply immediately or within 30 minutes after removal from the refrigerator. Return Valchlor to the refrigerator immediately after each use.
- Apply to completely dry skin at least 4 hours before or 30 minutes after showering or washing. Allow treated areas to dry for 5 to 10 minutes after application before covering with clothing.
- Emollients (moisturizers) may be applied to the treated areas 2 hours before or 2 hours after application.

- Do not use occlusive dressings on areas of the skin where Valchlor was applied.
- Avoid fire, flame, and smoking until Valchlor has dried.

8.3 Accountability

The PI must ensure that all drug supplies are kept under lock and key with access limited to those authorized by the investigator. The PI must maintain accurate records of the receipt of all study medication shipped by the Sponsor, including date received, lot number, expiration/re-test date, amount received and disposition of all study medication. Current dispensing records will be maintained and include date and amount of medication dispensed, initials of subjects receiving the medication, and any amount of medication not used or returned (or lost) by the subject. All remaining medication not required by regulation to be held by the clinical facility, must be destroyed following all appropriate regulatory guidelines or returned to the Sponsor immediately after the study is completed. Any lost, spilled or missing drug must be documented.

8.4 Prohibited Concomitant Therapy

Prior medications, going back 3 weeks from the screening date (systemic and topical), will be collected at the screening visit. Concomitant medications (systemic and topical) will be collected at each clinic visit. A detailed history of prior CTCL treatments will be collected.

The following drugs are **not allowed on treated lesions within 2 weeks** of enrollment or during the study:

- Topical steroids (including 1% hydrocortisone cream or ointment)

The following drugs are **not allowed within 3 weeks** of enrollment or during the study:

- Systemic steroids
- Psoralen UVA radiation therapy (PUVA)
- Narrow band-UVB
- Carmustine (BCNU)
- Other systemic therapies for CTCL

The following drugs are **not allowed within 30 days** of enrollment or during the study:

- 5-fluorouracil
- Vinblastine

- Dacarbazine
- ALA or 5-aminolevulinic acid
- Methyl-5-aminolevulinic acid
- Investigational drugs
- Drugs of abuse
- Agents known to cause photosensitization

The following drugs can only be used if there have been no phototoxic reactions to the stable dose of the drug after a minimum of 14 days of treatment:

- Quinolone antibiotic
- Tetracycline
- Sulfonamide
- Diphenhydramine
- Quinine
- Chloroquine
- Hydroxychloroquine
- Amiodarone
- Systemic nifedipine
- Quinidine
- Diltiazem
- Furosemide
- Thiazides
- Sulfonylureas
- Isotretinoin
- Acitretin

- Phenothiazines
- Tricyclic antidepressants

The following drugs are **not allowed within 2 months** of enrollment.

- Topical nitrogen mustard
- Valchlor

8.5 Compliance

Patients will be trained in the proper application of HyBryte and Valchlor. Application of HyBryte will be documented by site personnel by noting pink staining on lesions indicating application of the drug. Valchlor compliance will be determined by patient reports.

9 ADVERSE EVENTS

Timely, accurate and complete reporting and analysis of safety information from trials is crucial for the protection of subjects, investigators and the Sponsor, and is mandated by regulatory agencies worldwide. Soligenix has established standard operating procedures (SOPs) in conformity with regulatory requirements to ensure appropriate reporting of safety information. All trials that are the responsibility of Soligenix must be conducted in accordance with the procedures as provided below.

9.1 Definitions

9.1.1 **Adverse Experience (AE)**

Any noxious or unintended event that occurs in association with the use of an investigational agent in humans, *whether considered related to the investigational agent or not*. This definition encompasses symptoms or signs reported by the subject or detected by the Investigator or other competent observer, as well as medically important deviations from normality in the results of ancillary investigations. If present at time of first dose of study drug, such AEs must be recorded as part of the medical history.

9.1.2 **Treatment-Emergent AE**

An AE that is new in onset or aggravated in severity or frequency following entry into the study. In addition, any pathological finding on physical examination or diagnostic procedure that is new in occurrence or exacerbated in comparison with the subject's status at study entry is considered a treatment-emergent AE if it requires any medical or surgical intervention whatsoever (including, but not limited to, additional diagnostic procedures or alteration of prescribed therapy).

9.1.3 **Potentially Serious Adverse Experience**

Any AE that is sufficiently severe or alarming as to require any form of significant medical intervention. Note: Important medical events that may not result in death, be life threatening, or require hospitalization may be considered an SAE when, based upon appropriate medical judgment, they may jeopardize the subject and require medical or surgical intervention to prevent one of the outcomes listed in the SAE definition.

9.2 Relationship to Study Drug

The relationship of an AE to the assigned study drug is assessed using the following definitions:

Not Related: The drug experience is clearly related to other factors such as the patient's/subject's clinical state, therapeutic interventions or concomitant drugs.

Possibly Related: The drug experience follows a reasonable sequence from the time of drug administration and/or follows a known response pattern to the

study drug, but could have been produced by other factors such as the patient's/subject's clinical state, therapeutic interventions or concomitant drugs.

Related: The drug experience follows a reasonable temporal sequence from the time of drug administration and follows a known response pattern to the study drug, and cannot be reasonably explained by other factors such as the patient's/subject's clinical state, therapeutic interventions or concomitant drugs.

9.3 Severity of Adverse Event

A clinical determination of the intensity of an AE should be done for all reported AEs. The severity assessment for AEs should be completed using the following definitions as guidelines:

Mild: Awareness of sign or symptom, but easily tolerated.

Moderate: Discomfort enough to cause interference with usual activity.

Severe: Incapacitating with inability to work or do usual activity.

Not applicable: In some cases, an AE may be an “all or nothing” finding, which cannot be graded.

9.4 Recording Adverse Events

All AEs, whether judged to be related or not to the study drug, should be recorded in both the medical record and the CRF. If photographic evidence is available and relevant, it may be recorded. The start and resolution dates, the judgment of the severity of the AE, the judgment of the relationship of the AE to the study drug, the action taken for subsequent dose of study drug, and the outcome should be noted.

10 SERIOUS ADVERSE EVENT

10.1 Definition of Serious Adverse Event

A SAE is any event that meets any of the following criteria:

- Death
- Life-threatening
- Inpatient hospitalization or prolongation of existing hospitalization
- Persistent or significant disability/incapacity
- Congenital anomaly/birth defect in the offspring of a subject who received study drug
- Other: Important medical events that may not result in death, be life-threatening, or require hospitalization, may be considered an SAE when, based upon appropriate medical judgment, they may jeopardize the subject and may require medical or surgical intervention to prevent one of the outcomes listed in this definition.

Examples of such events are:

- Intensive treatment in an emergency room or at home for allergic bronchospasm
- Blood dyscrasias or convulsions that do not result in inpatient hospitalization
- Development of drug dependency or drug abuse

10.2 Definition of Terms

Life threatening: An AE is life threatening if the subject was at immediate risk of death from the event as it occurred; ie, it does not include a reaction that if it had occurred in a more serious form might have caused death. For example, drug induced hepatitis that resolved without evidence of hepatic failure would not be considered life threatening even though drug induced hepatitis can be fatal.

Hospitalization: AEs requiring hospitalization should be considered SAEs.

Hospitalization for elective surgery or routine clinical procedures that are not the result of AE (eg, elective surgery for a pre-existing condition that has not worsened) need not be considered AEs or SAEs. If anything untoward is reported during the procedure, that occurrence must be reported as an AE, either 'serious' or 'non-serious' according to the usual criteria.

In general, hospitalization signifies that the subject has been detained (usually involving at least an overnight stay) at the hospital or emergency ward for observation and/or

treatment that would not have been appropriate in the physician's office or outpatient setting. When in doubt as to whether 'hospitalization' occurred or was necessary, the AE should be considered serious.

Disability/incapacitating: An AE is incapacitating or disabling if the experience results in a substantial and/or permanent disruption of the subject's ability to carry out normal life functions.

10.3 Reporting Serious Adverse Events

When the Investigator, or trained designee, becomes aware that a serious or potentially serious AE (as defined above) has occurred, the site monitor or Medical Monitor must be notified **immediately** (and no later than 24 hours after notification) by telephone, regardless of the relationship (or lack thereof) of the AE to study therapy.

All reports of serious or potentially serious AEs must be followed within 24 hours (or sooner at the request of the Soligenix Medical Monitor) by the completion of a serious AE form signed by the investigator. This should be emailed to the site monitor and/or Medical Monitor.

In accordance with Soligenix SOPs and Health Authority regulations, investigators may be notified from time to time of the occurrence of serious, unexpected AEs. If such AEs are associated with the use of the study drug (ie, there is a reasonable possibility that the AE may have been caused by the drug) and are thus deemed significant new AEs or risks with respect to the drug, the investigator must promptly inform the relevant Institutional Review Board (IRB), in accordance with the ICH Guidance on Good Clinical Practices (E6, April 1996).

FOR ADVERSE EXPERIENCE REPORTING OR MEDICAL QUESTIONS THE MEDICAL MONITOR SHOULD BE CONTACTED:

[name]
Senior Vice President & Chief Medical Officer,
Study Medical Monitor
[REDACTED]
[REDACTED]
[REDACTED]

If above contact is not accessible, please call:

Soligenix, Inc., [name]
[contact]

FOR ADDITIONAL ASSISTANCE:

For additional assistance, please contact your clinical research monitor(s) OR

[name]
Medical Director

[REDACTED]
[REDACTED]
[REDACTED]

10.4 Overdose

Any instance of overdose (suspected or confirmed and irrespective of whether or not it involved HyBryte or Valchlor) must be communicated to Soligenix, Inc within 24 hours and be fully documented as an SAE. Details of any signs or symptoms and their management should be recorded including details of any antidote(s) administered.

11 STATISTICS

11.1 General Procedures

This is a randomized, pilot study assessing outcomes of patients receiving HyBryte compared to Valchlor in patients with stage IA, IB, and IIA CTCL. Subjects will be randomized to 12 weeks of treatment with either HyBryte or Valchlor in a 1:1 ratio. Additionally, the practical issues likely to arise in a larger clinical study comparing HyBryte to Valchlor will be identified. No formal efficacy statistics will be performed. Results will be presented as tables that include group means, standard deviations, medians, maximum, and minimum values for continuous variables and counts and percentages for dichotomous variables as well as individual patient listings.

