
Methodology: This will be an open-label trial enrolling patients with CTCL (stage IA, IB, or IIA) randomized to receive topical HyBryte or topical Valchlor for 12 weeks.
 
Patients randomized to HyBryte will apply the drug to all accessible lesions twice per week followed by visible light treatment 21 (± 3) hours later starting at 6 J/cm² and titrated up at each visit until there is evidence of mild erythema of the treated lesions following the light session (Grade 1 erythema on the Erythema Score) and dropping the light dose if there is Grade 2 erythema. Should the patient have Grade ≥ 3, treatment will be suspended for 1 week and treatment may be restarted at a 1 J/cm² lower than the last well-tolerated light dose.
 
Patients randomized to Valchlor will receive commercially available drug applied as per the package insert.
 
Three to 5 prospectively identified index lesions will be evaluated for mCAILS assessment and the lesions chosen will be representative of the patient's overall disease and, if the patient has both patch and plaque lesions, the index lesions should include each type in the approximate same percentage as their total lesions.
 
Patients will be treated for a total of 12 weeks, with follow-up visits at Week 13, Week 14, and Week 16/End of Study. Every three weeks, patients will come to the clinic for an assessment visit (ie, at Week 3, Week 6, Week 9, and Week 12). At these evaluation visits, a cumulative mCAILS, modified Severity-Weighted Assessment Tool (mSWAT), Physician Global Assessment (PGA), Skin Adverse Event Questionnaire (SAEQ) will be completed, and Scoring Dermatitis (SCORD) collected.
 
For HyBryte patients, these assessments will be done immediately prior to light treatment at the second light treatment visit of the evaluation week (ie, Weeks 3, 6, 9, 12).
 
Follow-up assessments will be conducted at Week 13 (1-week post-treatment), Week 14 (2 weeks post-treatment), and Week 16/End of Study (4 weeks post-treatment) and will also include mCAILS, mSWAT, PGA, SAEQ, and SCORD assessments.
 
Physical examinations and safety labs (hematology and chemistry) will be analyzed at Baseline, at the Week 12 assessment visit, and 4 weeks after completion of therapy (Week 16/End of Study). AE's will be recorded throughout the study. Vital signs will be collected at Baseline and Weeks 3, 6, 9, 12, 13, 14 and 16.
		

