4 STUDY PLAN

4.1 Study Design

This is a randomized, pilot study assessing outcomes of patients receiving HyBryte compared to Valchlor in patients with stage IA, IB, and IIA CTCL. Subjects will be randomized to 12 weeks of treatment with either HyBryte or Valchlor in a 1:1 ratio. Subjects randomized to HyBryte will apply HyBryte to all accessible lesions followed 21 (± 3) hours later by visible light treatment twice per week using the Daavlin 7 Series Phototherapy Device. Treatments will continue twice per week (at least 2 calendar days apart) for a total of 12 weeks of treatment (24 actual treatments). Patients randomized to Valchlor will receive treatment for 12 weeks with Valchlor following the directions in the FDA-approved package insert.

Patients will come to the clinic for an assessment visit at Baseline, Week 3, Week 6, Week 9, and Week 12. Patients will have mCAILS scores collected on their 3 to 5 index lesions, an mSWAT score, PGA, SAEQ completed, and a SCORD score collected.

For patients randomized to HyBryte, the assessments will be conducted immediately prior to light treatment at the second light treatment visit of the evaluation week (ie, Week 3, 6, 9, 12) immediately prior to the corresponding light treatment.

Patients will return to the clinic for follow-up visits and have assessments (mCAILS, mSWAT, PGA, SAEQ, and SCORD) at Week 13, Week 14, and Week 16/End of Study.

Safety laboratory assessments and physical exams will be done at Baseline, the Week 12 assessment visit, and the Week 16/End of Study visit. Vital signs will be collected at Baseline and Weeks 3, 6, 9, 12, 13, 14 and 16. Adverse events will be collected throughout the study.

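### By-visit SCORD means can understate Valchlor dermatitis in patients who had to stop treatment, and no planned summary counts those stops

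*Combined protocol and SAP*

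**What the plan says.** Section 2 makes a preliminary comparison of safety and efficacy after 12 weeks an objective. Section 3 lists the safety variables: SAEQ, SCORD, hematology, chemistry, physical examination, vital signs and adverse events. Interruption or reduction of treatment is not among them.

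Section 7.2.2 gives the reason for using SCORD: "this tool was modified to assess the severity of dermatitis in CTCL patients undergoing mechlorethamine treatment". Under sections 4.1 and 4.2 it is read at Baseline, at Weeks 3, 6, 9 and 12 on treatment, and at Weeks 13, 14 and 16 afterwards. No extra reading is described for the moment a patient stops drug.

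Section 8.2.4 stops Valchlor for any ulceration or blistering and for moderately severe or severe dermatitis. It continues: "Upon improvement, treatment with Valchlor can be restarted at a reduced frequency of once every 3 days". If that is tolerated for a week or more, use may rise to every other day for a week or more, and then to daily.

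For each adverse event, section 9.4 requires the dates, severity and relationship, and also that "the action taken for subsequent dose of study drug, and the outcome should be noted". Section 11.1 describes the output in general terms: "Results will be presented as tables that include group means, standard deviations, medians, maximum, and minimum values for continuous variables", counts and percentages for dichotomous variables, and individual listings.

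**The concern.** The reactions that SCORD was adapted to measure are the ones that take a Valchlor patient off daily dosing, and the absence can last about as long as the gap between two readings. The next scheduled score may then describe a patient who is off drug or on reduced use and already better. It enters the visit mean as an ordinary value, with nothing to show why it is low.

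The other instruments do not restore the peak in a summary. The SAEQ looks back 24 hours. The skin grading around each light session (section 7.2.1) is for the HyBryte arm only, and Valchlor patients have no scheduled clinic visit between the three-weekly ones. Adverse event severity in section 9.3 is judged by interference with activity, with the lowest grade defined as "Awareness of sign or symptom, but easily tolerated". A small blister could carry that grade and still stop treatment.

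At stake is the comparative safety objective. With about 5 patients per arm, one or two missed peaks can change what a table of visit means appears to show.

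**Working it through.** The documents state no figure on this point, so there is none to reproduce.

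**Inputs**
- Spacing of on-treatment SCORD readings: 21 days (Weeks 3, 6, 9, 12; sections 4.1 and 4.2).
- Minimum step-up before daily Valchlor resumes: 7 + 7 = 14 days (section 8.2.4).
- Days from stopping to improvement, h: not given, so a range is shown.
- Assumptions: drug is stopped when the reaction starts, visits are exactly 21 days apart, and onset is uniform within the interval.

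**Formulas**
- Time off daily use is at least h + 14 days.
- Chance that the next SCORD falls on stopped or reduced dosing: min(1, (h + 14)/21).
- Chance that the next SCORD falls after improvement: 1 − h/21, for h up to 21.

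These are different events. The first includes the h days when the reaction is still active, so it rises with h. The second falls with h, and only the second measures a missed peak.

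| h (days) | Days off daily use | On stopped or reduced dosing | After improvement |
|---|---|---|---|
| 1 | 15 | 71% | 95% |
| 3 | 17 | 81% | 86% |
| 5 | 19 | 90% | 76% |
| 7 | 21 | 100% | 67% |
| 10 | 24 | 100% | 52% |
| 10.5 | 24.5 | 100% | 50% |
| 14 | 28 | 100% | 33% |

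For example, at h = 3 the values are 17/21 = 81% and 1 − 3/21 = 86%. A simulation of onsets over the 84 treatment days, with visits on days 21, 42, 63, 84, 91, 98 and 112, agreed with both formulas to within 0.002.

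For h of 7 or more, the 100% needs no assumption about onset, because a period of 21 days or longer must contain a visit. The break-even for a missed peak is 1 − h/21 = 0.5, which gives h = 10.5 days.

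**If 2 of about 5 Valchlor patients react independently**, the chance that both are next scored only after improvement is (1 − h/21)²: 73% at h = 3, 44% at h = 7, 27% at h = 10 and 11% at h = 14.

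**Can the planned tables recover the peak?** The maximum in section 11.1 reads as the largest value across patients in a group. It is taken over scheduled scores, so it cannot show a peak that was never scored. The action taken on dosing is recorded under section 9.4, but neither section 3 nor section 11.1 names a summary of it.

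**The case against.** The strongest reply is that the information is not lost. Adverse events are a listed safety variable, collected throughout, with dates, severity and action on dosing. Section 11.1 promises individual listings, and about 5 patients per arm can be read one by one. Section 11.1 is also generic, so a table it does not name could still be produced. This stands in part: the gap lies in the planned summaries, not in the data. Even so, a reader of the tables would see SCORD means without the stops that explain them.

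A reader might infer that peaks are usually missed. That depends on h, which the documents do not give. If improvement takes longer than 10.5 days, the next score more often catches the active reaction.

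A reader might also set the Valchlor figure of 81% (at h = 3) against 7/21 = 33% for a one-week HyBryte suspension and conclude that the comparison is tilted toward Valchlor. The two figures are not alike. The first counts reduced dosing and the second does not, although the synopsis has HyBryte restarting at a lower light dose. HyBryte SCORD is also read before the light session, so it leaves out that session's immediate reaction. The net direction is therefore open.

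The argument from adverse event grading is narrow. It fits the any-grade ulceration and blistering triggers, and fits poorly with dermatitis showing marked redness and edema. The section 9.3 definitions are offered as guidelines. Finally, the step-up wording is permissive and section 8.2 lets the package insert prevail, so the 14 days is the minimum under the protocol's own text.

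**Conclusion.** The point holds as a reporting gap. By-visit SCORD means can understate Valchlor dermatitis in patients who had to stop, and no safety variable or planned summary reports the stops that would reveal it. The next score after a stop falls on stopped or reduced dosing with probability 81% at h = 3 days, and with certainty from 7 days. It falls after improvement with probability between 86% (h = 3) and 33% (h = 14).

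These figures rest on uniform onset (except the 100% from 7 days), stopping at onset, the 14-day minimum step-up and an unstated h. The size of the understatement in SCORD points cannot be derived, because the documents give no peak or post-improvement scores. The follow-up readings at Weeks 13, 14 and 16 come after treatment and do not recover on-treatment peaks.

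**What to change.** Change the reporting only, and leave every dosing and stopping rule as it is. Add to the section 3 safety variables and the section 11.1 tables, by arm:

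1. The number and percentage of patients with at least one stop, suspension or reduction for a skin reaction, taken from the section 9.4 action-taken field, with duration where adverse event dates or patient reports allow.
2. Each patient's highest on-treatment SCORD (Weeks 3 to 12), beside the visit means.

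In the patient listings, mark dosing status (full, reduced or held) next to each SCORD and SAEQ value. Do not summarize by that status, since about 5 patients per arm is too few to split.

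The cost is a few table rows and a listing column, with no new visit or procedure. Valchlor compliance rests on patient report (section 8.5), so dosing status may need one added CRF field. The highest scheduled SCORD still misses peaks between visits, which is why the count of stops must stand beside it.
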